### **2.8 Planned subgroup analyses**

We have selected sub-group criteria using simple data available in primary care. We will run confirmatory sub-group analyses on fracture outcomes for the following:

- **Age:** We will examine whether interventions are best targeted to the oldest old ( $\leq 80$  years or  $\geq 81$  years).
- **Gender:** There is considerable excess risk of falling and fracture in women.
- **Previous history of falls in the last 12 months:** This is not well recorded in primary care, and hence will depend on self-report;
- **Frailty:** This will be based on the categorisation of the Strawbridge questionnaire - not frail (rarely or never/sometimes) versus frail (often/very often).

- **Cognitive impairment:** If there are sufficient numbers of people scoring less than 5 on the cognitive impairment sub-test, we will run a sub-group analysis with cut-points less than 5 or 5 or more.

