## 5. OUTCOMES OF THE TRIAL

OUTCOMES	TIME POINT collected at	SCORING
Primary outcome		
Fall related fractures	Over the 18 months (Baseline, 4, 8, 12 and 18 months).	Fall fracture rates (per person per month observation) This will be obtained by estimating the rate over 18 months and fractioning this as a monthly rate
Secondary outcomes		
Additional fracture parameters		
 
• Proportion (and number) of people sustaining at least one fracture over the study period will be obtained. Thus, the derived variable will be binary (patient with at least one fracture =1/ no fracture =0).
 
• Time to first fracture
 
• Fracture rates and proportions for data extending beyond 18 months
 

Falls (CRF)	Over the 18 months (Baseline, 4, 8, 12 and 18 months)	
 
• Fall rates (per person per month observation)
 
• Proportion (and number) of people sustaining at least one fall over the study period.
 

Falls (Diary)		

Analysed at 4, 8, 12 For sensitivity analyses only	Baseline, 4, 8, 12 months	
 
• Fall rate (per person per month observation)
 
• Proportion (number) of people sustaining at least one fall
 

Frailty Strawbridge Questionnaire	Baseline and 18 months	
To summarise, the frailty questionnaire is Strawbridge 1998 with the four domains: physical, nutritional, cognitive and sensory. The score of this based on a 4 –point ordinal scale (rarely or never / sometimes /often /very often).
 
We will analyse overall and sub-domain scores

Mobility	Baseline, 4, 8, 12 and 18 months	Questions on difficulty in balancing on level surface, ability to walk outside of the house and average time spent walking.
EQ-5D	Baseline, 4, 8, 12 and 18 months	Evaluates patients QOL based on 5 dimensions converted into a single summary score (range: -0.57 to 0 (death) to 1 (perfect health state)).The ED-5D will be scored using the devised algorithm (EuroQol Group, 1990) and summarised as detailed in the User Guide (EuroQol Group, 2005).
SF-12	Baseline, 4, 8, 12 and 18 months	Scoring of the SF-12 will be carried out using ‘the SF-12v2- How to Score version 2 of the SF-12 Health Survey’ manual (Ware et al.1996).
Predictor variables		

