### 6.1.2 Nested Intention to treat

In a nested analysis we will present our finding just for those at intermediate/high risk of falling. We will establish the risk score of falling, using the baseline questions which are analogous to those on the Balance Screener but enable us to identify the at risk population across all three arms. The reason for using the baseline questionnaire is to ensure the risk score is available for all patients including those on the control arm as well as those on the interventions.

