#### *6.3.2. Outcomes*

##### *6.3.2.1 Covariates to adjust in the statistical models*

The covariates that will be used to adjust for in the statistical models will be corresponding baseline variable, deprivation score (for the GP practice), age and gender.

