##### *6.3.2.2 Primary outcome*

Fracture rate (per person per month) observation has a skewed distribution (heavy skewed in favour of zeros). We will explore the possible models that may account for this skew: (a) Poisson model; (b) zero inflated Poisson model; (c) negative binomial; (d) zero inflated negative model.

For the fracture rate (per person per month observation), we will assess this over the 18 months, using an 'offset' variable in the appropriate model, and also incorporate the general practice variable as the random effect.

Proportion of patients having at least one fracture, will be analysed using logistic regression models, with the random effect as general practice. The adjusted analysis will incorporate the appropriate covariates (as stated above).

Time to first fracture will be assessed using survival analysis methods.

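### The covariate list for the fracture models does not name falls history, which the trial already collects by self-report; pre-specifying it would be a small, free gain in precision.

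*SAP*

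**What the plan says.** SAP section 6.3.2.1 gives one list of covariates for the statistical models: "corresponding baseline variable, deprivation score (for the GP practice), age and gender". Section 6.3.2.2 refers back to it for fractures: "The adjusted analysis will incorporate the appropriate covariates (as stated above"). The fracture rate model is also to "incorporate the general practice variable as the random effect", and the logistic model for the proportion with a fracture has the same random effect. Time to first fracture is left to survival methods, with no further detail.

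Falls history appears elsewhere. Section 2.8 names "Previous history of falls in the last 12 months" among the sub-group factors for fracture outcomes and comments: "This is not well recorded in primary care, and hence will depend on self-report". Section 6.4 brings sub-group factors in through a treatment-by-covariate interaction, in models separate from the main analysis.

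The outcome table in section 5 gives the timing of the primary outcome as "Over the 18 months (Baseline, 4, 8, 12 and 18 months"), and gives falls the same timing. It defines no baseline fracture variable.

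On allocation, section 2.4 describes blocks of three practices, no stratification, and minimisation with no balancing factors named. Section 2.7 plans 60 practices of 150 participants.

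**The concern.** The phrase about a corresponding baseline variable works for outcomes with a baseline measurement, such as EQ-5D or SF-12. For fractures it has no defined referent. Its most natural meaning is prior fracture, but it could also mean prior falls, or nothing. So the SAP does not clearly place falls history in the fracture models, although it treats that variable as relevant enough to fractures to plan a sub-group analysis on it.

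With 20 practices per arm, any tendency of fallers to cluster by practice makes the chance difference between arms larger than in an individually randomised trial of the same size. Adjusting for a prognostic baseline variable removes the matching part of the error from the estimate. Fixing the choice in advance also avoids a debate after unblinding about whether an imbalance in the baseline table calls for adjustment. Some precision and credibility are at stake, but not validity.

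**Working it through.** **1. The plan's own figures (section 2.7).** For 6% v 4%, two-sided 5%, 80% power, pooled variance:

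n = [1.96 × √(2 × 0.05 × 0.95) + 0.842 × √(0.06 × 0.94 + 0.04 × 0.96)]² / 0.02² = 1,863 per arm. The SAP states 1,900, which is 2% away, so the figure reproduces. The stated inflation is 2,600/1,900 = 1.368. At 150 per practice this implies an ICC of 0.368/149 = 0.0025, inside the stated 0.001 to 0.003. Practices per arm: 60/3 = 20.

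**2. Standard error of the log rate ratio.** 9,000/3 = 3,000 per arm; 10% loss leaves 2,700, or 135 per practice. At ICC 0.003 the design effect is 1 + 134 × 0.003 = 1.402, so the effective n is 2,700/1.402 = 1,926 per arm. Using the planning risks as a stand-in for the rate:

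SE = √[0.94/(0.06 × 1,926) + 0.96/(0.04 × 1,926)] = 0.144. At ICC 0.001 it is about 0.13.

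**3. Size of a chance imbalance.** The SAP gives none of the inputs needed. Assumed ranges are: prior fallers p = 0.30 to 0.35; practice-level ICC of falls history 0.01 to 0.03; fracture rate ratio r = 1.5 to 2.5 for fallers against non-fallers.

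- SD of the difference between two arms: d = √[2p(1−p)(1 + 149 × ICC)/3,000]
- Shift in the log rate ratio from a one-SD imbalance: ln{[1 + (p + d/2)(r−1)] / [1 + (p − d/2)(r−1)]}

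| p | ICC | r | SD of difference | Shift at 1 SD |
|---|---|---|---|---|
| 0.30 | 0.01 | 1.5 | 0.019 | 0.008 |
| 0.35 | 0.01 | 1.5 | 0.019 | 0.008 |
| 0.30 | 0.03 | 2.5 | 0.028 | 0.029 |
| 0.35 | 0.03 | 2.5 | 0.029 | 0.028 |

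The planned effect is ln(4/6) = −0.405.

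**4. What adjustment would buy.** The share of the variance due to falls-history imbalance is (0.008/0.144)² = 0.3% at the low end and (0.029/0.144)² = 4% at the high end. Removing it reduces the SE by 1 − √(1 − 0.003) = 0.2% to 1 − √(1 − 0.04) = 2%.

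**5. Wider assumptions.** With 25-40% prior fallers, ICC 0.001-0.05 and r from 1.5 to 3, the SD of the arm difference is 1.2 to 3.7 percentage points. The one-SD shift is 0.005 to 0.043, and the 95% bound on the distortion of the rate ratio is a factor of 1.01 to 1.09. The middle case (30%, 0.01, r = 2) gives 1.9 points and a factor of 1.03. Even at the top, (0.043/0.15)² = 8% of the variance, so the SE would fall by 1 − √(1 − 0.08), or about 4%.

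**The case against.** The strongest reply is that nothing here is an error. The SAP pre-specifies sensible covariates, which may absorb part of any imbalance in falls history. The practice random effect in the rate and proportion models carries between-practice variation into the standard error. Choosing a variable for sub-group analysis does not oblige anyone to adjust for it. All of this stands, and it is why the point is only an improvement.

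Several stronger readings are tempting but not supported:

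- **That imbalance is left uncorrected, or that the result is biased.** Chance imbalance in an omitted covariate does not bias a randomised comparison or invalidate its test. It is only not directly adjusted for.
- **That falls history already defines risk in this trial.** Section 6.1.2 says only that risk is scored "using the baseline questions which are analogous to those on the Balance Screener". The SAP does not give their content, so that they ask about past falls is an inference. The sub-group plan carries the point alone.
- **That the list definitely excludes falls history.** The primary outcome is labelled as fall-related fractures in section 5, and falls share its time points, so prior falls cannot be ruled out as the intended variable. The term is undefined.
- **That the error could reach 40% of the SE.** A two-SD imbalance at the top of the assumed ranges does give 2 × 0.029/0.144 = 40%. But that is a rare draw, and the SE already allows for such draws.
- **That a count of falls is available.** Section 2.8 mentions only a history of falls, so a scale of none, one, or two or more cannot be presumed.

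Missing self-report is a fair worry, since the SAP gives no estimate of it; it calls for a stated rule.

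**Conclusion.** The point holds as a free improvement. Falls history is not a named covariate for the fracture models, the corresponding baseline variable is undefined for fractures, and a 12-month self-report is already planned for use with these outcomes. Leaving it out costs a little precision and some face validity: up to about 2% of the standard error under the main assumptions, and about 4% under the widest. These sizes rest on assumed faller prevalence, clustering of falls history and prognostic strength. They also use the planning risks of 6% and 4% in place of the fracture rate. No stated figure in the SAP changes.

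**What to change.** In section 6.3.2.1, for the adjusted fracture models (rate, proportion, and time to first fracture):

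- add self-reported falls in the 12 months before baseline, in the form in which it was collected, alongside age, gender and practice deprivation;
- state whether this is the corresponding baseline variable for fractures;
- keep participants with a missing answer in the model through a missing category, so that none are dropped.

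The change should be made before unblinded analysis. It costs a few sentences of SAP wording and one extra model term, with no new data collection. Section 2.4 has participants enrolled before their practice is randomised; it should be confirmed that the baseline answer was also given before allocation.

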##### *6.3.2.2 Primary outcome*

Fracture rate (per person per month) observation has a skewed distribution (heavy skewed in favour of zeros). We will explore the possible models that may account for this skew: (a) Poisson model; (b) zero inflated Poisson model; (c) negative binomial; (d) zero inflated negative model.

For the fracture rate (per person per month observation), we will assess this over the 18 months, using an 'offset' variable in the appropriate model, and also incorporate the general practice variable as the random effect.

Proportion of patients having at least one fracture, will be analysed using logistic regression models, with the random effect as general practice. The adjusted analysis will incorporate the appropriate covariates (as stated above).

Time to first fracture will be assessed using survival analysis methods.

#### 6.3.2.3. Secondary outcome: falls data

Falls data and falls rate will be summarised and statistical assessed in a similar way to the primary outcome.

#### 6.3.2.4. Secondary outcome: Diary card data – falls data

Diary card falls data will be summarised and statistical assessed in a similar way to the primary outcome.

#### 6.3.2.5. Secondary outcome: EQ 5D

The items of the EQ-5D will be summarised for each of the interventions and time-points.

The EQ -5D score will be summarised using mean, standard deviation, median and range values. The mean difference (and the 95% of the mean difference) between treatment arms will be reported. Both adjusted and unadjusted random effect linear regression models will be fitted to the data.

#### 6.3.2.6. Secondary outcome: SF-12

The mental and physical components of the SF-12 will be summarised using mean, standard deviation, median and range values. The mean difference (and the 95% of the mean difference) between treatment arms will be reported. Both adjusted and unadjusted random effect linear regression models will be fitted to the data.

#### 6.3.2.7. Secondary outcome: Strawbridge Questionnaire

For each of the four domains of the Strawbridge Questionnaire we will summarise the data into will be summarised into binary categories (rarely or never/sometimes) and (often/very often).

Both adjusted and unadjusted random effect logistics regression models will be fitted to the data.

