### ***Secondary outcomes***

Secondary outcomes will encompass the following:

- *Fracture rate per person month of observation for the entire available period of observation*

We have collected additional data on fractures from HES for a time period that extends beyond 18 months after randomisation. This data will also be summarised and analysed.

- Proportion of people sustaining one or more fracture over 18 months

- Time to first fracture

We will attempt to date all fractures. The date of fracture will be taken as the A&E attendance or HES episode admission date where these exist. In addition, we will check GP records for confirmation of fracture dates where these are recorded, with the exact date of fracture event if reported taking precedence over HES and A&E attendance if these differ.

- Fracture episodes

It is possible that people will experience multiple fractures from one fall. It will not be possible to consistently attribute fractures to a single fall event. Instead we will estimate fracture episodes. We will characterise all the fractures occurring on the same date as one episode. We will use statistical modelling to account for fractures occurring in the same individual and in the same episode. We will report and explore the number of episodes of fractures and recurrent fracture episodes. We may not be able to generate sufficient resolution in the data to assign fractures to episode. If so, we will not report these data (this will be apparent after the data cleaning is finalised).

- Fracture regions

We will estimate the difference in number of proximal femoral fractures (hip fractures) and fractures involving the distal radius (wrist fractures). Hip fractures were defined as verified fractures with a specific description of neck of femur or proximal femur. Fractures described as subtrochanteric, femoral shaft, distal femur, or simply femoral will not be categorised as hip fractures.

- Falls rate per person per month observation over the 18 months

- Proportion of people sustaining one or more fall over the 18 months
- mobility/ADLs:  
Questions on difficulties balancing on a level surface, ability to walk outside of the house, and average time spent walking.
- Frailty:  
A 16 item frailty questionnaire. We will report sub-domains and the overall domain scores for the follow up time points in which we have these data.
- Cognitive ability:  
A clock-drawing test used as for cognitive screening.
- Health related quality of life:  

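### Frailty is promised as overall and domain scores, but the analysis section models only four dichotomised domains, leaves the overall score unanalysed and does not state how the binary category is formed

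*SAP*

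**What the plan says.** Four places in the SAP deal with frailty.

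- **Section 2.6, Secondary outcomes.** The instrument is "A 16 item frailty questionnaire". The commitment is: "We will report sub-domains and the overall domain scores for the follow up time points in which we have these data".
- **Section 5, outcome table.** The questionnaire has "four domains: physical, nutritional, cognitive and sensory" and is collected at baseline and 18 months. The score rests on a four-point "ordinal scale (rarely or never / sometimes /often /very often"). The entry closes: "We will analyse overall and sub-domain scores".
- **Section 6.3.2.7, Strawbridge Questionnaire.** Each of the four domains is put into "binary categories (rarely or never/sometimes) and (often/very often"). Adjusted and unadjusted random-effect logistic models follow. No overall score is mentioned.
- **Section 2.8, sub-groups.** Frailty is one of the sub-groups for confirmatory analyses of fracture outcomes. People are split as "not frail (rarely or never/sometimes) versus frail (often/very often"). Section 6.4 then calls for a formal interaction test.

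**The concern.** Two things look wrong.

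First, the outcome definition and the analysis section describe different analyses. Sections 2.6 and 5 commit to scores, including an overall score. Section 6.3.2.7 commits to four binary domain variables and nothing else. An analyst who follows 6.3.2.7 to the letter leaves a stated outcome unanalysed and gives up information that the trial already collects.

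Second, the binary category is expressed in the four response options, while the questionnaire has 16 items in four domains. The SAP states no rule that takes several responses to one value per domain, or to one frail/not-frail label per person. The second gap reaches the fracture analysis, because the same split defines a sub-group whose interaction test is called confirmatory. If the rule is settled late, the membership of that sub-group is open to choice.

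**Working it through.** **1. The passages side by side.** The SAP gives no SD, prevalence, effect size or power for frailty, so there is no figure of its own to reproduce.

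| Place | Domains | Overall score | Form |
|---|---|---|---|
| 2.6 Secondary outcomes | yes | yes | scores |
| 5 Outcome table | yes | yes | scores, to be analysed |
| 6.3.2.7 Strawbridge | yes | not mentioned | binary, logistic |
| 6.3.2.7 Other secondary outcomes (number used twice) | – | – | names mobility/ADLs only |

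No other section analyses frailty as an outcome. By contrast, 6.3.2.5 (EQ-5D) and 6.3.2.6 (SF-12) give mean differences and random-effect linear models for scores.

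**2. Information kept by a binary split of a roughly normal score.** Let p be the share above the cut (assumed; not in the SAP), z_p the matching normal quantile and φ the normal density. The relative efficiency is φ(z_p)² / [p(1 − p)].

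- p = 0.5: 0.3989² / 0.25 = 0.637, loss 36%
- p = 0.3: 0.3477² / 0.21 = 0.576, loss 42%
- p = 0.2: 0.2800² / 0.16 = 0.490, loss 51%
- p = 0.1: 0.1755² / 0.09 = 0.342, loss 66%
- p = 0.05: 0.1031² / 0.0475 = 0.224, loss 78%

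The smallest possible loss is at the median cut: 1 − 2/π = 36.3%.

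**3. Information kept against the four-level ordinal response.** For a cumulative model, the information is Σ (d_k − d_{k−1})² / p_k. Here p_k is the share in category k, and d_k is the latent density at the k-th cut point, taken as 0 at both ends. Example with four equal categories and a logistic latent scale: d = 0, 0.1875, 0.25, 0.1875, 0.

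- Four levels: 2 × (0.1875² + 0.0625²) / 0.25 = 0.3125
- Two levels: 2 × 0.25² / 0.5 = 0.25
- Ratio 0.80, loss 20%

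| Assumed shares, lowest to highest category | Loss, probit | Loss, logit |
|---|---|---|
| 0.05 / 0.45 / 0.45 / 0.05 | 21.8% | 8.3% |
| 0.10 / 0.40 / 0.40 / 0.10 | 26.5% | 13.8% |
| 0.25 / 0.25 / 0.25 / 0.25 | 26.0% | 20.0% |
| 0.40 / 0.30 / 0.20 / 0.10 | 31.0% | 30.0% |
| 0.50 / 0.30 / 0.15 / 0.05 | 37.7% | 43.2% |
| 0.60 / 0.25 / 0.10 / 0.05 | 41.1% | 50.1% |
| 0.70 / 0.20 / 0.07 / 0.03 | 46.5% | 58.4% |

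**4. How much the unstated rule matters.** I simulated 400,000 people answering a four-item domain. Four items is an assumption: 16 items over four domains is 16/4 = 4 on average, and the SAP does not give the split. Items share a latent normal variable with correlation 0.3 or 0.5. A share q of responses falls in the upper two categories, a quarter of it in the top one, and 25% of responses fall in the second-lowest category. The entries are the share of people classed positive, for correlation 0.3 / 0.5.

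| Rule | q = 0.2 | q = 0.1 |
|---|---|---|
| Any item in the upper two | 50.3% / 44.6% | 29.4% / 25.9% |
| At least two items | 21.3% / 22.1% | 8.2% / 9.7% |
| Mean score 2.5 or more | 14.1% / 17.0% | 5.6% / 7.9% |
| All four items | 1.5% / 3.3% | 0.3% / 0.9% |

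Each rule is compatible with the SAP's wording, and they give very different groups.

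**The case against.** Five points can be made for the plan.

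- **The scoring may be settled elsewhere.** Section 5 names a published instrument, and Section 2.8 refers to that questionnaire's categorisation. The source or the protocol, neither at hand, may supply the rule. This stands. The missing rule would be a gap in detail on its own; it is raised here alongside the contradiction about the scores.
- **The cut may not be an item-level cut.** Section 5 attaches the four-point scale to the questionnaire's score, not expressly to an item. If domain scores lie on that scale, the split does classify a domain. A reader might infer that the split cannot be applied to a domain or a person at all. The documents do not support that: any stated aggregation rule would make it workable. What can be said is that it is not defined as written.
- **The information loss is not a fixed figure.** A reader might infer that a third or more of the information is necessarily lost. That holds only against a roughly normal score, and the SAP gives no frailty distribution. Against a four-level response some losses in step 3 are well below a third.
- **A two-group split is a legitimate sub-group choice.** Section 2.8 says it prefers simple data available in primary care. This stands, which is why the fix keeps a two-group rule and only asks that it be stated.
- **Frailty is one of several secondary outcomes.** This also stands and limits the weight of the point.

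None of these supplies an analysis of the overall score or reconciles Section 5 with 6.3.2.7.

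**Conclusion.** The contradiction holds on the text alone. Sections 2.6 and 5 promise overall and domain scores; the Strawbridge section analyses four dichotomised domains and no section analyses the overall score. The domains themselves are kept, so what is lost outright is the overall score, and what is weakened is the domain analysis.

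The size of that weakening is conditional: 36% to 78% for a roughly normal score with 50% down to 5% of people above the cut, and about 8% to 58% against a four-level ordinal response in the distributions tried. All of these shares are assumptions.

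The rule from 16 items to a domain category or a person-level label is not stated in the SAP. Under the simulated assumptions, plausible rules class anywhere from about 2% to 50% of people as positive when 20% of responses are in the upper two categories. That matters most for the frailty sub-group, because it is called confirmatory.

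The importance is modest. The point does not touch the primary fracture analysis, and no effect on power for frailty can be derived from the SAP.

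**What to change.** In Section 6.3.2.7 (Strawbridge Questionnaire):

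- State or cite how the domain and overall scores are formed from the 16 items, including how missing items are handled.
- Analyse the 18-month overall score and each domain score with a linear model that has practice as random effect, or an ordinal model if the distribution requires it. Adjust for the baseline score and the other covariates in 6.3.2.1 (practice deprivation, age and gender).
- Keep the binary version as a descriptive table with its rule stated.

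In Section 2.8, state one person-level frailty rule based on the same baseline score and fix it before unblinding. An interaction with the continuous baseline score may be added as a supporting analysis; it assumes a linear relation, so it should not replace the stated split.

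The cost is SAP wording only, since Section 5 already has frailty collected at baseline and 18 months. The downside is that a mean score difference is less direct to explain than a proportion, and the descriptive table covers that need.
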